3.2.2 Secondary endpoints

- Time to recovery defined as satisfying one of the following two categories from the 7-point ordinal scale (Day 1-Day 29):
 - not hospitalized, no limitations of activities;
 - not hospitalized, limitation of activities, home oxygen requirement, or both.
- Proportion of patients with recovery at Days 7, 14, 29 and 60.
- Proportion of patients with improvement (from Day 1) of one category using the 7-point ordinal scale at Days 7, 14 and 29.
- Proportion of patients with improvement (from Day 1) of two categories using the 7-point ordinal scale at Days 7, 14 and 29.
- All-cause mortality at Days 29 and 60.
- Proportion of patients alive and not in with respiratory failure (invasive mechanical ventilation or extracorporeal membrane oxygenation [ECMO]) at Day 29.
- Proportion of patients needing re-hospitalization over 60 days.
- Duration of hospitalization from Day 1 (Day 1 - Day 29; measured in days).

- Mean change from baseline in 7-point ordinal scale (Days 7, 14 and 29).
- Total time on supplemental oxygen (Day 1 - Day 29; measured in days).
- Incidence and duration of new non-invasive ventilation or high flow oxygen use (Day 1 - Day 29; measured in days).
- Incidence and duration of new oxygen use (Day 1 - Day 29; measured in days).
- Incidence and duration of new mechanical ventilator use (Day 1 - Day 29; measured in days).
- Proportion of patients receiving invasive mechanical ventilation or extracorporeal membrane oxygenation (ECMO) at Days 7, 14 and 29 (7-point ordinal scale criteria #6).

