Discharge	The patient is discharged and leaves the hospital alive. This does not include if a patient is moved to another unit.
	The time to discharge = the elapsed time (in days) from Day 1 to the earliest day at which the patient is Discharged from hospital (= Day where the 7-point ordinal scale score is equal to 1 or 2).
Improvement in	A decrease from baseline of at least one point in the 7-point ordinal score (eg, 5
clinical status	to 4).
Worsening	An increase from baseline of at least one point in the 7-point ordinal scale score
clinical status	(eg, 5 to 6).

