7.2 Endpoints

Clinical study endpoints and associated definitions are listed in Table 5. Additional definitions are included in Section 8. Analysis tables are included in Section 9.3, Section 9.4 and Section 9.5.

Table 5. Clinical study RPL554-COV-201 endpoint definitions.

Endpoints	•	Definitions
Primary Refer to Section 9,	The proportion of patients who are in recovery state at Day 29.	Clinical status assessed using the 7-point ordinal scale score.
Table 10		The proportion of patients in each treatment arm that meet the definition of recovery.
		Recovery = one of the following two categories from the 7-point ordinal scale: 1. not hospitalized, no limitations of activities; 2. not hospitalized, limitation of activities, home oxygen requirement, or both.
Secondary Refer to Section 9,	Time to a recovery state (Day 1-Day 29; measured in days)	Clinical status assessed using the 7-point ordinal scale score.
Table 11		Time to recovery = elapsed time (in days) from Day 1 to the first day on which patients satisfy either 1 or 2 category listed in the primary endpoint.
	Proportion of patients who are in a recovery state at Days 7, 14 and 60.	Clinical status assessed using the 7-point ordinal scale score.
		The proportion of patients in each treatment arm that meet the definition of recovery.
		Recovery = one of the following two categories from the 7-point ordinal scale:

pg. 14 Confidential

Endpoints		Definitions
		not hospitalized, no limitations of activities; not hospitalized, limitation of activities, home oxygen requirement, or both.
	Proportion of patients with improvement of one category using the 7-point ordinal scale	Clinical status assessed using the 7-point ordinal scale score.
	(Day 1 - Days 7, 14 and 29).	The proportion of patients in each treatment arm that meet the definition of a one category improvement in clinical status.
		Improvement in clinical status = a decrease from baseline of one point in the 7-point ordinal score (eg, 5 to 4).
	Proportion of patients with improvement of two	Clinical status assessed using the 7-point ordinal scale score.
	categories using the 7-point ordinal scale (Day 1 - Days 7, 14 and 29).	The proportion of patients in each treatment arm that meet the definition of a two category improvement in clinical status.
		Improvement in clinical status = a decrease from baseline of two points in the 7-point ordinal score (eg, 5 to 3).

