9.4 Secondary Endpoint Analysis

Patients that die in the study will be handled as worst case in all analyses.

To have an evaluation using all patients we will count an event as the type of need or worse (eg, patients with oxygen need; non-invasive ventilator need; ventilator need; or with death at time of evaluation will be counted as having data supporting oxygen need), and included in both denominator and numerator (refer to Section 8.5).

9.4.1 Time to a recovery state (Day 1 - Day 29; measured in days)

The time to recovery from Day 1 to Day 29 will be compared between treatment groups using a log-rank test; patients not in recovery at end-of study/withdrawal will be censored at last observed time point in the treatment period or at last time status was assessed if collected post treatment-withdrawal. Patients with death as outcome will be censored at the scheduled end-of-study Day 29. Data will be illustrated using Kaplan-Meier plots and the median time to recovery estimated if appropriate. Stratification in the model with respect to COVID disease severity will be done if the randomization outcome has sufficient numbers in each group with respect to these characteristics.

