p-value Enrolled Ensifentrine Placebo (log-(N=45) (N=30) (N=15) rank)

Days to recovery

Mean (SD)

Median (Min. - Max.)

n = number of patients with recorded value

pg. 49 Confidential

^{*} Recovery = one of the following two categories from the 7-point ordinal scale:

^{1.} not hospitalized, no limitations of activities;

^{2.} not hospitalized, limitation of activities, home oxygen requirement, or both.

Table 14.2.6: Proportion of patients in recovery* from initiation of study medication, ITT

		Enrolled (N=45)	Ensifentrine (N=30)	Placebo (N=15)
Recovery through Day 60	n			
	Yes			
	No			
Recovery Day 1 - Day 7	n			
	Yes			
	No			
Recovery Day 1 - Day 14	n			
	Yes			
	No			

n = number of patients with recorded value

^{*} Recovery = one of the following two categories from the 7-point ordinal scale:

^{1.} not hospitalized, no limitations of activities;

^{2.} not hospitalized, limitation of activities, home oxygen requirement, or both.

Table 14.2.7: Proportion of patients with improvement of one category using the 7-point ordinal scale from initiation of study medication, ITT

		Enrolled (N=45)	Ensifentrine (N=30)	Placebo (N=15)
One Category Improvement, Day 1 - Day 7	n	,	,	•
	Yes			
	No			
One Category Improvement, Day 1 - Day 14	n			
	Yes			
	No			
One Category Improvement, Day 1 - Day 29	n			
	Yes			
	No			

Improvement = A decrease from baseline of at least one point in the 7-point ordinal score (or discharge, whichever was first)

pg. 51 Confidential

Table 14.2.8: Proportion of patients with improvement of two categories using the 7-point ordinal scale from initiation of study medication, ITT

		Enrolled (N=45)	Ensifentrine (N=30)	Placebo (N=15)
Two Categories Improvement, Day 1 - Day 7	n	•		
	Yes			
	No			
Two Categories Improvement, Day 1 - Day 14	n			
	Yes			
	No			
Two Categories Improvement, Day 1 - Day 29	n			
. , ,	Yes			
	No			

Improvement = An increase from baseline of at least one point in the 7-point ordinal scale score (or discharge, whichever was first)

pg. 52 Confidential

Table 14.2.9: All-cause mortality, ITT

	Ensifentrine (N=30)	Placebo (N=15)
Reason of death at Day 29	0 (0%)	
Reason of death at Day 60	0 (0%)	

Table 14.2.10: Proportion of patients Alive and not in Respiratory Failure* from initiation of study medication, ITT

Proportion of Patients	Proportion of Patients Alive and not in		Placebo
Respiratory Failure (Scales less than 6)		(N=30)	(N=15)
Day 1 - Day 7	n		,
	Yes		
	No		
Day 1 - Day 14	n		
-	Yes		
	No		

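### SAP shell 14.2.8 defines two-category improvement with the SAP's own wording for worsening, so as written it counts deaths as improved; Table 5 omits 'at least', so read literally it leaves out a 4-to-1 recovery

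*SAP*

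**What the plan says.** The endpoint is a secondary one. Protocol 3.2.2 lists it as "Proportion of patients with improvement (from Day 1) of two categories using the 7-point ordinal scale at Days 7, 14 and 29". It gives no rule for patients who improve by more than two categories.

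The SAP defines improvement in several places:

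- **Section 7.1, Table 4.** Improvement in clinical status is a fall of at least one point from baseline. Worsening is "An increase from baseline of at least one point in the 7-point ordinal scale score".
- **Section 7.2, Table 5.** The one-category endpoint is "a decrease from baseline of one point in the 7-point ordinal score (eg, 5 to 4"). The two-category endpoint is "a decrease from baseline of two points in the 7-point ordinal score (eg, 5 to 3").
- **Section 14, shell 14.2.7 (one category).** "Improvement = A decrease from baseline of at least one point in the 7-point ordinal score".
- **Section 14, shell 14.2.8 (two categories).** The title is "Table 14.2.8: Proportion of patients with improvement of two categories using the 7-point ordinal scale from initiation of study medication, ITT". The footnote is "Improvement = An increase from baseline of at least one point in the 7-point ordinal scale score", followed by a parenthesis about discharge.

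Section 9.4 adds: "Patients that die in the study will be handled as worst case in all analyses".

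**The concern.** The footnote to shell 14.2.8 repeats Table 4's definition of worsening under a title that promises improvement. It is wrong in direction (increase instead of decrease) and in threshold (one point instead of two). Correcting the direction alone would turn 14.2.8 into a copy of 14.2.7.

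Falling back on Table 5 does not fully settle the endpoint. Its wording can be read as exactly two points, and no text in either document says at least two. For the one-category endpoint, Table 4 and shell 14.2.7 make the intent clear; the two-category endpoint has no such support.

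Three reported proportions are at stake. Section 9.4.2 compares them between arms by logistic regression, with an adjusted difference in proportions and a confidence interval, so a wrong definition carries through to the estimated treatment difference. Programmed from the footnote, the table would present worsening, deaths included, as improvement. Programmed literally from Table 5, the best outcome open to a patient would count as a failure.

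**Working it through.** The plan states no figure for this endpoint, so there is none to reproduce. The check is to list, for each eligible baseline score, which later scores each written rule counts as improved.

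**Inputs**

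- Scale 1 to 7, with 7 = death (SAP Tables 4 and 5).
- Eligible baseline scores b = 3, 4 or 5 (Protocol 5.1).
- Planned arm sizes 30 and 15 (Protocol 6.1).

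**Rules, for a later score s**

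- Footnote to 14.2.8: s − b ≥ 1 (identical to Table 4 worsening).
- Table 5 two-category row, read literally: b − s = 2.
- At least two: b − s ≥ 2.

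| Baseline | Footnote 14.2.8 | Table 5 literal | At least two |
|---|---|---|---|
| 3 | 4, 5, 6, 7 | 1 | 1 |
| 4 | 5, 6, 7 | 2 | 1, 2 |
| 5 | 6, 7 | 3 | 1, 2, 3 |

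At every baseline the footnote counts death and shares no score with the at-least-two rule. From baseline 4 those two rules disagree on five of the seven scores (1, 2, 5, 6, 7). Table 5 read literally differs from at-least-two on score 1 only from baseline 4, and on scores 1 and 2 from baseline 5. Table 5's literal one-category rule (b − s = 1) counts only score 3 from baseline 4, so a 4-to-1 patient would meet neither endpoint.

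**Which baseline matters.** The header of shell 14.1.5b gives 44 enrolled patients at baseline 4, out of 45. Its arm Ns (1 and 0) do not add up to 44, so only the total is used here.

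**Effect of one patient.** 1/30 = 3.3 points; 1/15 = 6.7 points.

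**Illustration.** These Day 29 scores are assumed and are not trial data; every patient starts at 4.

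- Ensifentrine (30): 14 at score 1, 13 at 2, 1 at 4, 1 at 6, 1 dead.
- Placebo (15): 6 at score 1, 6 at 2, 2 at 6, 1 dead.

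| Rule | Ensifentrine | Placebo | Difference |
|---|---|---|---|
| At least two | 27/30 = 90.0% | 12/15 = 80.0% | +10.0 points |
| Table 5 literal | 13/30 = 43.3% | 6/15 = 40.0% | +3.3 points |
| Footnote 14.2.8 | 2/30 = 6.7% | 3/15 = 20.0% | −13.3 points |

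Shell 14.2.9 is pre-filled with 0 (0%) deaths for ensifentrine. Moving the assumed ensifentrine death to score 6 leaves every percentage unchanged, because the footnote counts 6 and 7 alike and the other two rules count neither.

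**Range for the literal Table 5 rule.** Let all patients start at 4, let R be the proportion recovered (score 1 or 2), and let f be the share of those at score 1. The literal proportion is R(1 − f). For R = 0.90 it is 0.90, 0.45 and 0 at f = 0, 0.5 and 1.

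**The case against.** The strongest reply is that the footnote sits in an example shell while the operative definitions are in Section 7. Tables 4 and 5 both define improvement as a decrease, the shell's own title and row labels say improvement of two categories, and Section 9.4 treats deaths as worst case. A programmer would have to disregard all of these to count a death as improved. That is fair: the harm arises only if the footnote is followed. But SAP Section 4 presents the samples as tables planned for the final analyses, and the SAP states no rule that the body prevails over the shells. Even with correct programming, the footnote could be carried into the report and mislabel the result.

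Second, the recovery tables offer a cross-check. From baseline 4, at-least-two counts scores 1 and 2, which is exactly the SAP's definition of recovery, and recovery is tabulated separately in shells 14.2.3 and 14.2.6. With 44 of 45 at baseline 4 and the other patient at baseline 3 (shell 14.1.5a), a correct 14.2.8 could differ from those tables by at most one patient. A reversed table would visibly conflict with them, and Figure 3 and the score listings could also expose it. This lowers the chance of a lasting error but does not correct the definition.

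Third, exactly two is a strained reading of Table 5, given that Table 4 and both shell footnotes use 'at least'. This has force, and the Table 5 point is best treated as a clarification. It is still needed, because those places fix the threshold at one point and none says at least two.

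The discharge parenthesis does not rescue the footnote. It looks like a time window, as in other shells. Read as a criterion, it would add discharged patients but still count scores 5, 6 and 7.

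**Conclusion.** The concern holds. As written, the 14.2.8 footnote measures worsening, includes death at every eligible baseline, and has no overlap with two-category improvement. This follows from the scale and the written rules without any assumption. The Table 5 point rests on a literal reading; under it, a 4-to-1 patient is left out, as are 5-to-2 and 5-to-1.

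Three exploratory secondary proportions are affected. The actual number of misclassified patients cannot be derived from the documents. The illustration shows that the sign of the treatment difference can reverse, but that depends on the assumed scores. The footnote is most likely a copy error, and the primary endpoint is unaffected. It should be corrected because it is an endpoint definition attached to a planned output.

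**What to change.** Make three wording changes in the SAP:

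1. Shell 14.2.8 footnote: *Improvement = a decrease from baseline of at least two points in the 7-point ordinal scale score.*
2. Table 5, two-category row: *a decrease from baseline of at least two points.*
3. Table 5, one-category row: *a decrease from baseline of at least one point*, to agree with Table 4 and shell 14.2.7.

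With these edits the scores counted as two-category improvement are 1 from baseline 3; 1 and 2 from baseline 4; and 1, 2 and 3 from baseline 5. Death is never counted. No new data or analysis is needed. If the SAP is already final, describe the correction in the clinical study report, as SAP Section 4 allows.

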	All-cause mortality at Days 29 and 60.	Clinical status assessed using the 7-point ordinal scale score.
		Death = 7-point ordinal scale score is equal to 7 or using a vital records search returns a death record, the date on the record will be the date of death.
	Proportion of patients alive and not in respiratory failure (invasive mechanical	Clinical status assessed using the 7-point ordinal scale score.
	ventilation or extracorporeal membrane oxygenation (ECMO)) at Days 7, 14 and 29.	The proportion of patients in each treatment arm that meet the definition of alive and not is respiratory failure.
		Alive and not in respiratory failure (invasive mechanical ventilation or ECMO) = 7-point ordinal scale score is equal to 1, 2, 3, 4 or 5.
	Proportion of patients needing re-hospitalization (post-dose Day 1 – Day 60).	Assessed following discharge: the eCRF question regarding re-hospitalization will be used at Day 29 and Day 60 follow-up contact.
		The proportion of patients in each treatment arm that meet the definition of re-hospitalization following discharge.
		Re-hospitalization = following their treatment with study medication and subsequent discharge from hospital, they were re-admitted to a hospital for COVID related issue(s).

pg. 15 Confidential

Endpoints		Definitions
	Total time of hospitalization	Clinical status assessed using the 7-point
	between Day 1 - Day 29 (measured in days).	ordinal scale score.
	(Hospitalized = # days where the 7-point ordinal scale score is equal to 3, 4, 5 or 6.
		Or 7-point ordinal scale score is equal
		to 7 if patient dies while hospitalized
		between Day 1-29.
	Change from baseline in 7-	Clinical status assessed using the 7-point
	point ordinal scale (Days 7, 14 and 29).	ordinal scale score.
		The mean change from baseline of the 7-point
		ordinal scale in each treatment arm as
	Total time on supplemental	assessed by the statistical analysis. Clinical status assessed using the 7-point
	oxygen (Day 1 - Day 29; measured in days).	ordinal scale score.
	. ,	Hospitalized patient supplemental oxygen = # days where the 7-point ordinal scale score is equal to 4, 5, or 6.
		 Or 7-point ordinal scale score is equal to 7 if patient dies while hospitalized between Day 1-29.
		Not hospitalized patient supplemental oxygen = # days where the 7-point ordinal scale score is equal to 2 (if required to have home oxygen).

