	Total time of non-invasive ventilation or high flow oxygen use (post-dose Day 1	Clinical status assessed using the 7-point ordinal scale score.
	- Day 29; measured in days).	Non-invasive ventilation or high flow oxygen use = # days where the 7-point ordinal scale score
		is equal to 5 or 6. • Or 7-point ordinal scale score is equal to 7 if patient dies while hospitalized between Day 1-29.
	Proportion of patients alive and with oxygen use at Days 7, 14 and 29	Clinical status assessed using the 7-point ordinal scale score.
	,	The proportion of patients in each treatment arm that meet the definition of requiring oxygen use.
		Hospitalized patient supplemental oxygen = the 7-point ordinal scale score is equal to 4, 5, or 6. • Or 7-point ordinal scale score is equal
		to 7 if patient dies while hospitalized between Day 1-29.
		Not hospitalized patient supplemental oxygen = the 7-point ordinal scale score is equal to 2 (if required to have home oxygen).
	Proportion of patients alive at Days 7, 14 and 29 with non-	Clinical status assessed using the 7-point ordinal scale score.

pg. 16 Confidential

Endpoints		Definitions
	invasive ventilation or high flow oxygen use	The proportion of patients in each treatment arm that meet the definition of requiring non-invasive ventilation/high-flow oxygen use.
		Non-invasive ventilation or high flow oxygen use = the 7-point ordinal scale score is equal to 5 or 6. • Or 7-point ordinal scale score is equal to 7 if patient dies while hospitalized between Day 1-29.
	Proportion of patients alive and receiving invasive mechanical ventilation or extracorporeal membrane oxygenation (ECMO) at Days 7, 14 and 29).	Clinical status assessed using the 7-point ordinal scale score. The proportion of patients in each treatment arm that meet the definition of requiring invasive mechanical ventilation.
		The 7-point ordinal scale score is equal to 6. • Or 7-point ordinal scale score is equal to 7 if patient dies while hospitalized between Day 1-29.
Safety Refer to Section 9, Table 12	Incidence of Adverse Events (AEs).	Number of AEs and number of patients with AEs for all TEAEs and for subcategories of AEs (SAEs, severe AEs, fatal AEs etc). Incidence = proportion of patients in each treatment arm that experience an adverse

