8.5 Missing Data

All attempts will be made to collect all data per protocol.

 The patients withdrawn from treatment will be followed up regarding their status according to the 7-point ordinal scale at Day 29 as far as possible (exceptions for patients with withdrawn consent or lost to follow-up) and this data will be the primary source for handling missing data in the study.

Any data point that appears to be erroneous or inexplicable based on clinical judgment will be investigated as a possible outlier.

• If data points are identified as outliers, sensitivity analyses may be performed to examine the impact of including or excluding the outliers. Any substantive differences in these analyses will be reported.

For survival analyses, patients with death as outcome will be censored at Day 29 (Day 60), unless the required event was reached prior to death. Patients who are lost to follow-up or terminate the study prior to Day 29 (Day 60) for other reason than death and prior to observing/experiencing the event will be censored at the time of their last observed assessment.

The only time to event analyses is the time to recovery.

For secondary endpoint analyses, the following imputation rules will be used for patients who are lost to follow-up, terminate early from the study, or do not have further outcome data available after discharge for any reason than death:

- Patients with no data collected at the actual time point of interest for other reason than
 death, the last assessment of their status prior to this time point will be used as a
 representative for that time point. Especially, if the patient's clinical status scale is 1 or 2
 at the last observed assessment, then the patient will be considered to be recovered
 through Day 29.
- For endpoints assessing total time (oxygen or non-invasive ventilator care), the status for patients with no data collected for other reason than death, will be assumed unchanged from last assessment of the score up to last day in the definition of the endpoint (Day 29). Thus, no extra days will be added for patients without oxygen or patients without non-invasive ventilator care at last assessment.
- Patients that die in the study will be handled as worst case in all the analyses, that is they are considered to be on oxygen need, non-invasive and invasive mechanical ventilator need for all time points following the death.

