9.4.6 Duration of hospitalization (Day 1 - Day 29; measured in days)

The total number of days with recorded use will be the sum of all reported days, regardless of whether the days occur consecutively or in disjoint intervals. Results will be summarized by descriptive statistics including medians and quartiles by treatment arm and compared between treatment groups using Wilcoxon rank sum test.

Summaries of the results of the secondary analyses are displayed in Table 11.

Table 11. Clinical study RPL554-COV-201 analysis tables - Secondary Analyses.

Table #	Table Name	Table Contents
14.2.5	Time to recovery, Day 1 - Day 29	Overall and by Treatment group
14.2.6	Proportion of patients in recovery at Day 60, ITT	Overall and by Treatment group Day 1 – Day 7 Day 1 – Day 14
14.2.7	Proportion of patients with improvement of one category using the 7-point ordinal scale from Day 1, ITT	Overall and by Treatment group Day 1 – Day 7 Day 1 – Day 14 Day 1 – Day 29
14.2.8	Proportion of patients with improvement of two categories using the 7-point ordinal scale from Day 1, ITT	Overall and by Treatment group Day 1 – Day 7 Day 1 – Day 14 Day 1 – Day 29
14.2.9	All-cause mortality, ITT	Overall and by Treatment group At Day 29 At Day 60
14.2.10	Proportion of patients alive and not in respiratory failure (invasive mechanical ventilation or extracorporeal membrane oxygenation (ECMO) at Day 29, ITT	Overall and by Treatment group Day 1 – Day 7 Day 1 – Day 14
14.2.11	Summary of the proportion of patients re- hospitalized following initiation of study medication and subsequent discharge (over 60 days), ITT	Overall and by Treatment group
14.2.12	Duration of hospitalization from Day 1 (Day 1 - Day 29; measured in days), ITT	Overall and by Treatment group
14.2.13	Change from baseline in 7-point ordinal scale at Days 7, 14 and 29, ITT	Overall and by Treatment group Baseline – Day 7 Baseline – Day 14 Baseline – Day 29
14.2.14	Total time on supplemental oxygen (Day 1 - Day 29; measured in days), ITT	Overall and by Treatment group
14.2.15	Total time of non-invasive ventilation or high flow oxygen use (post-dose Day 1 - Day 29; measured in days).	Overall and by Treatment group
14.2.16	Summary of the proportion of patients with oxygen use at Days 7, 14 and 29, ITT	Overall and by Treatment group
14.2.17	Summary of the proportion of patients with non-invasive ventilation or high flow oxygen use at Days 7, 14 and 29), ITT	Overall and by Treatment group

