Day 1 - Day 29	n		
-	Yes		
	No		

pg. 54 Confidential

⁽or discharge, whichever was first)
*7-point ordinal scale score = 1, 2, 3, 4 or 5. n = number of patients with recorded value

Table 14.2.11: Summary of Proportion of patients re-hospitalized following initiation of study medication and subsequent discharge (over 60 days), ITT

Proportion of Patients	Re-hospitalized	Enrolled (N=45)	Ensifentrine (N=30)	Placebo (N=15)
Day 1 - Day 60	ay 1 - Day 60 n			
	Yes			
	No			

n = number of patients with recorded value

Table 14.2.12: Duration of hospitalization from initiation of study medication (Day 1 - Day 29 (or discharge, whichever was first); measured in days), ITT

Days of hospitalization	Enrolled		Placebo p-value*
from Day 1	(N=45	(N=30)	(N=15)
Median (Q1 - Q3)			

^{*}Wilcoxon rank sum test

Hospitalized = # days where the 7-point ordinal scale score = 3, 4, 5 or 6.

Discharge = The patient is discharged and leaves the hospital alive.

pg. 56 Confidential

Table 14.2.13: Change from Baseline in 7-point Ordinal Scale at Days 7, 14, and 29, ITT

Change from 7-point Ordin	n Baseline in nal Scale	Enrolled (N=45)	Ensifentrine (N=30)	Placebo (N=15)
Day 7	n Mean (SD)	()	()	()
Day 14	n Mean (SD)			
Day 29	n Mean (SD)			

Computed from Day 1 scale minus Day 7, Day 14, and Day 29 scale accordingly (or discharge) (or discharge, whichever was first)

pg. 57 Confidential

Table 14.2.14: Total time on Supplemental Oxygen (Day 1 - Day 29; measured in days), ITT

Days of Suppl	emental Oxygen	Enrolled	Ensifentrine	Placebo
(Scale=4)		(N=45)	(N=30)	(N=15)
Day 1 - 29	Median (Q1 - Q3)			

Hospitalized patient: 7-point ordinal scale score = 4, 5, or 6. Or 7-point ordinal scale score is equal to 7 if patient dies while hospitalized between Day 1-29.

Not hospitalized patient supplemental oxygen = # days where the 7-point ordinal scale score is equal to 2 (if required to have home oxygen).

pg. 58 Confidential

Table 14.2.15: Total time of non-invasive ventilation or high flow oxygen use (post-dose Day 1 - Day 29 (or discharge, whichever was first); measured in days)

Days of non-invasive ventilation or High Flow Oxygen Use (Scale=5)		Enrolled (N=45)	l Ensifentrine (N=30)	Placebo (N=15)
Day 1 - 29	Median (Q1 - Q3)			

Non-invasive ventilation or high flow oxygen use = # days where the 7-point ordinal scale score is equal to 5 or 6. Or 7-point ordinal scale score is equal to 7 if patient dies while hospitalized between Day 1-29.

pg. 59 Confidential

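### Several SAP example shells and three Table 5 labels contradict the SAP's own rules for deaths and for the safety composite (minor)

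*SAP*

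**What the plan says.** **Hospital days.** In SAP Table 5 (Section 7.2), total time of hospitalization counts days at scores 3 to 6, and the definition also extends "to 7 if patient dies while hospitalized" within Days 1 to 29. SAP 9.4 adds: "Patients that die in the study will be handled as worst case in all analyses". SAP 9.4.6 has the totals "compared between treatment groups using Wilcoxon rank sum test". The footnote of shell 14.2.12 reads "Hospitalized = # days where the 7-point ordinal scale score = 3, 4, 5 or 6" and has no score-7 clause.

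**Oxygen and ventilation proportions.** Table 5 labels three proportions as concerning living patients: oxygen use, non-invasive ventilation or high-flow oxygen, and invasive ventilation or ECMO. The last begins "Proportion of patients alive and receiving invasive mechanical ventilation". Under each label the definition adds "Or 7-point ordinal scale score is equal to 7 if patient dies while hospitalized between Day 1-29". SAP 8.5 says of patients who die that "they are considered to be on oxygen need, non-invasive and invasive mechanical ventilator need for all time points following the death". SAP 9.4 counts death as need: "or with death at time of evaluation will be counted as having data supporting oxygen need), and included in both denominator and numerator". Shells 14.2.16 to 14.2.18 keep *alive* in their titles, and their footnotes stop at score 6.

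**Safety composite.** Table 5 measures time from Day 1. SAP 8.7 censors patients who complete follow-up without an event at their Day 29 visit. SAP 9.5 asks for a log-rank test and a stratum-weighted difference in proportions. Shell 14.3.1 has a Yes/No row, then a time row measured from consent that its footnote restricts to patients with adverse events. It shows no log-rank result and no difference.

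**The concern.** The shells are what a programmer builds from, and here they give different answers from the text.

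- In 14.2.12 the patient with the worst outcome gets one of the shortest stays, so an early death favours its own arm.
- In 14.2.16 to 14.2.18 a death lowers the apparent need for support, where the text says it should raise it.
- In 14.3.1 the time row drops every censored patient and starts the clock before treatment, so it is not a summary of the quantity that the log-rank test compares.

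The SAP does not settle a difference between shell and text by an explicit rule. It also weakens its own case for the third item: 8.5 says that recovery is the sole time-to-event analysis, although 8.7 and 9.5 plan a second.

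**Working it through.** The plan states no figure on this point, so there is none to reproduce. The inputs are 30 and 15 patients (SAP 6.1), follow-up to Day 29, and a screening window of 0 to 4 days before Day 1 (Protocol 1.3). Numbers and days of events are assumptions.

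**1. Hospital days (14.2.12).** For a patient never discharged who dies on Day d, the shell counts d − 1 days. If score-7 days run through Day 29, Table 5 gives 29. Death on Day 5 is therefore 4 days against 29.

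- Null SD of the Wilcoxon U, ignoring ties: √(30 × 15 × 46 / 12) = √1725 = 41.53.
- A placebo death can move from below to above at most 30 ensifentrine stays: 30 / 41.53 = 0.72 in z. An ensifentrine death can pass at most 15 placebo stays: 15 / 41.53 = 0.36.
- Assumed example: three ensifentrine stays at each length from 2 to 11 days (the study days listed in shell 14.2.2). A placebo death with 2, 6 or 10 days counted by the shell shifts U by 28.5, 16.5 or 4.5, so z by 0.69, 0.40 or 0.11.
- If only the day of death counts as a score-7 day, the stay grows by one day and U shifts by 0.5 × (3 + 3) = 3, so z by 0.07. The number of score-7 days therefore matters, and Table 5 does not give it.

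**2. Proportions (14.2.16 to 14.2.18).** Take one placebo death and x other patients with the need.

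- Text: (x + 1)/15. Shell: x/15, or x/14 if *alive* also removes the death from the denominator.
- Difference: 1/15 = 6.7 percentage points, or (14 − x)/210, which is at most 14/210 = 6.7.
- For ensifentrine: 1/30 = 3.3, or (29 − x)/870, at most 29/870 = 3.3.

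**3. Safety composite (14.3.1).** If consent falls in the screening window, it adds 0 to 4 days per patient. To show the effect of dropping censored patients, assume ensifentrine events on Days 3, 5 and 7 (3 of 30), and all event-free patients censored at Day 29:

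| Placebo event days | Yes/No row | Time row (median, from Day 1) | Log-rank z | p |
|---|---|---|---|---|
| 3, 5, 7 | 10% v 20% | 5 v 5 | 0.92 | 0.355 |
| 3, 4, 5, 6, 7 | 10% v 33% | 5 v 5 | 1.95 | 0.051 |
| 2, 3, 4, 6, 7, 8 | 10% v 40% | 5 v 5 | 2.41 | 0.016 |
| 2, 3, 4, 5, 6, 7, 8 | 10% v 47% | 5 v 5 | 2.86 | 0.004 |

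The time row does not change, while the planned test goes from unremarkable to clear. The Yes/No row does change.

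**The case against.** The best defence is that the SAP already says where definitions live. Section 7.2 points to Table 5 and Section 8, the Preface speaks of sample tables, and Section 14 is headed as examples. A reader might infer that the plan leaves the handling of deaths open. The documents do not support that for oxygen and ventilation: 8.5 and 9.4 are explicit, Protocol 10.5.1 counts death as oxygen need and as ventilator need, and SAP Table 11 lists outputs 14.2.16 to 14.2.18 without *alive*. The labels and shells are wrong, but the rule is not in doubt.

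A reader might also infer that shell 14.3.1 would hide a difference between arms. It would not, because the Yes/No row shows the event fractions. Shell footnotes say that all randomized patients were of moderate severity. If so, there is one stratum, and the stratum-weighted difference is the raw difference between those fractions. Several other shells also omit a required comparison, and SAP 12 allows additions, so a missing p-value alone is weak evidence. Nor is Day 60 in Table 5 a clear contradiction: it can be a wider descriptive window around the Day 29 test.

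What remains is narrower. SAP 12 permits extra output, not a different event definition, time origin or analysis set. Omitting score 7 is not shell shorthand, since shells 14.2.14 and 14.2.15 print the clause. For hospital days, 8.5 spells out no rule, so counting through Day 29 is inferred from the general worst-case sentence.

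**Conclusion.** The inconsistencies are real and should be corrected, but the point is minor. Shell 14.2.12, shells 14.2.16 to 14.2.18, shell 14.3.1 and three Table 5 labels do not match the SAP's definitions. The fourth *alive* endpoint, alive and not in respiratory failure (scores 1 to 5), is consistent.

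The first two items matter only if patients die by Day 29. Shell 14.2.9 shows 0 (0%) for ensifentrine and nothing for placebo, which may be a placeholder, so the practical effect cannot be determined. The bounds in z use the untied null SD and the through-Day-29 reading. The third item needs no deaths, but its size rests on assumed event times.

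Nothing here supports an inference about the primary result: recovery at Day 29 does not use these definitions. All affected outputs are exploratory secondary or safety outputs of an unpowered pilot, tested without multiplicity adjustment.

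**What to change.** 1. Add the score-7 clause to shell 14.2.12, and state in Table 5 how many score-7 days count. Through Day 29 is the reading that fits the worst-case rule in 9.4.
2. Remove *alive* from the three Table 5 labels and from the titles of shells 14.2.16 to 14.2.18, and add score 7 to their footnotes. Reconcile the in-hospital limit on deaths in Table 5 and in shells 14.2.14 and 14.2.15 with the unrestricted rule in 8.5.
3. Rebuild the time part of shell 14.3.1: Day 1 as origin, all safety-set patients, Kaplan-Meier estimates with numbers censored, the log-rank p-value, and the difference in proportions with its confidence interval (proportions only if there are no events, as 9.5 says). Label any Day 60 summary separately from the Day 29 test. In 8.5, say that the sentence naming recovery as the sole time-to-event analysis refers to efficacy.
4. While these shells are open, reconcile the cut-off at discharge in their titles with 9.4.6, which sums separate intervals of hospital stay, and with the rule that counts home oxygen at score 2, which arises only after discharge.

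The cost is wording in Table 5 and 8.5 and edits to shell rows, titles and footnotes. No new data are needed, no follow-up is dropped, and the primary analysis is unchanged.
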